### **Treatment B**

Children on treatment B will also stay in the NRU for a stabilisation period of 7 days during which their mothers or caretakers will have learnt preparation of khichuri and halwa and taking care of the children at home. Dietary therapy, micronutrient supplementation, training of mothers or caretakers, immunization, and anti-helminthic treatment will be the same as in treatment A. Thereafter, they will be discharged and advised to attend the NFU every week for one month and then at fortnightly intervals until they achieve an oedema-free WH >80%. If a child develops an acute illness or the general condition is not satisfactory at the time of discharge, then the discharge will be postponed till resolution of the illness. The protocol for follow-up will be the same as in treatment A, the difference being that the children will be

brought to the NFU by the parents. If a child fails to attend the NFU within 2 days of a specified follow-up day, a health worker will make a home visit, do the follow-up and reiterate the importance of bringing the child to the NFU for follow-up. The health worker, in course of her follow-up, will try to find out the reason(s) for defaulting. A previous study conducted at the NRU [12] to find out the cause of defaulting showed the principal reason to be the wrong perception of the parents that follow-up was not needed since the child was okay. Other reasons that came up during the previous study, and that will also be inquired during the follow-up visit by the health worker in this study, include: inability of the mother to come to the hospital alone, illness of the mother or child, distance, visit to village homestead, inability to leave other children at home alone, inability to afford the travel expenses, and death of the child.

### **Treatment C**

Children on treatment C will remain admitted in the NRU until they have achieved an oedema-free WH >80%, and have a good general condition. This will typically involve a stay in the NRU for 15-25 days. The standardized feeding schedule will be followed and micronutrient supplements provided until discharge (refer to treatment A). Training of mothers or caretakers, immunization, and anti-helminthic therapy will be the same as in treatment A, except that in this treatment schedule the mothers or caretakers will receive more educational lessons due to their longer stay in the NRU. Morbid conditions occurring during rehabilitation, including diarrhoea, pneumonia, or septicemia will be recorded in precoded forms. After being discharged from the NRU, the children in this group will be advised to attend the NFU at intervals of two weeks for one month, and then at monthly intervals until they achieve a WH >90%. The entire family will be encouraged to come for the follow-up visit during which preparation of khichuri and halwa will be demonstrated to the mothers and then served to all members. Health education of the mothers or caretakers will be reinforced. Iron supplementation will be continued for 2 months in usual doses. Intercurrent illnesses such as diarrhoea or pneumonia will be treated.

### **Sample Size**

A preliminary analysis of 51 severely malnourished children (WH <70%) who received nutritional rehabilitation in our NRU after recovering from diarrhoea showed that the weight gain was  $8.4 \pm 7.3$  g/kg.day, and the time to achieve WH >80% was  $22.5 \pm 6.2$  days. In designing a trial with three or more groups, it is suggested that pair-wise comparisons between groups of central interest be first decided upon [13]. It is assumed that the proposed method of home-based nutritional rehabilitation with outpatient follow-up will result in a relatively lesser weight gain of 4 g/kg per day, will require approximately 35 days to achieve WH >80%, and lead to a 35% reduction in cost of treatment. Sample sizes of 58, 15, and 24 children in each group (hospital and home-based) were calculated from the assumptions of weight gain, time to achieve WH >80%, and reduction in cost of treatment respectively.

The formula used for calculating sample size is:

$$\frac{2 (SD)^2}{WD^2} \times \text{factor for } \alpha, \beta$$

where, SD is the standard deviation, WD is the worthwhile difference, power of detection is 90%, and type I error is 0.05. Taking the greatest of the three calculated sample sizes and allowing for 20% dropouts (refusal to continue, unexpected migration of the family to an outlying area, or later diagnosed to have tuberculosis), a sample size of 75 children in each group has been estimated.

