### **Hypothesis to be tested:**

1. After an initial period of hospitalization, severely malnourished children recovering from diarrhoea can be managed at home using indigenous, low-cost, and culturally acceptable diets.
2. The cost-benefit of a home-based programme for nutritional rehabilitation of severely malnourished children recovering from diarrhoea will be more than the conventional hospital-based programme.

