## Data Analysis

Describe plans for data analysis. Indicate whether data will be analyzed by the investigators themselves or by other professionals. Specify what statistical softwares packages will be used and if the study is blinded, when the code will be opened. For clinical trials, indicate if interim data analysis will be required to monitor further progress of the study. (TYPE WITHIN THE PROVIDED SPACE).

Data will be analyzed using the SPSS Windows software. The Epi Info software will be used to calculate anthropometric indices. Enrollment characteristics will be compared between the three treatment groups. The outcome variables will be compared both within and between groups from enrollment to discharge. For normally distributed quantitative variables, means will be compared by ANOVA. Variables not normally distributed will be log transformed before analysis. Categorical variables will be compared by Chi-square test, multiple or logistic regression will be performed to minimise bias if required.

Results from all randomized children will be included in the analysis of the study. Data from children withdrawn because of failure to respond, TB, or voluntary dropout will be included in the analysis upto the time of withdrawal. A supplementary analysis excluding the children withdrawn may also be made.

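### Hypothesis 1 is a claim that home care is adequate, but the trial is sized to detect an assumed home-care shortfall, with no criterion linking the two and 90% power supported for B v C only

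*Protocol*

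**What the plan says.** The first hypothesis (Protocol, Hypothesis to be tested) is that, after an initial hospital stay, "severely malnourished children recovering from diarrhoea can be managed at home using indigenous, low-cost, and culturally acceptable diets". It gives no comparator, margin or minimum acceptable result. The second is comparative: the cost-benefit of the home programme "will be more than the conventional hospital-based programme".

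Sample Size starts from 51 children treated in the unit, in whom "weight gain was $8.4 \pm 7.3$ g/kg.day" and time to reach the weight-for-height target was 22.5 days (SD 6.2). It then sets out what is expected of one home arm only, treatment B: this "will result in a relatively lesser weight gain of 4 g/kg per day", will take about 35 days, and will cut cost by 35%. No assumption is given for treatment A, home care with home follow-up. The result is "Sample sizes of 58, 15, and 24 children in each group" for weight gain, time and cost in that order, with "power of detection is 90%, and type I error is 0.05". The largest of the three, allowing for 20% dropout, becomes 75 per group. The difference entered in the formula is described as a worthwhile one to detect, not as a margin to exclude.

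Data Analysis states: "For normally distributed quantitative variables, means will be compared by ANOVA". It covers three groups and also plans within-group comparisons.

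**The concern.** The hypothesis and the calculation that fixes the trial's size point in opposite directions. The hypothesis would be supported by showing that home care does well enough. The calculation gives a high chance of showing that it does worse, by an amount the protocol already expects. With no criterion for well enough, neither outcome of the weight-gain or time test answers Hypothesis 1. Significance in the assumed direction means slower recovery at home. Non-significance leaves open a loss as large as the difference the protocol itself calls worthwhile.

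The power statement has a related gap. The section cites advice to decide first which pairs are of central interest, but then gives figures for B v C only. A third of the children are allocated to A, and the 90% does not automatically carry over to A v C or to the three-group test.

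**Working it through.** **Inputs, all from Sample Size.** C: mean 8.4, SD 7.3 g/kg per day. B: mean 4. Difference 8.4 - 4 = 4.4. Power 90%, type I error 0.05. Sidedness is not stated; two-sided reproduces the printed figure (one-sided gives 48). The factor for two-sided 0.05 and 90% is (1.960 + 1.282)² = 10.51.

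**The plan's own figure.** n = 2 × SD² / WD² × factor = 2 × 7.3² / 4.4² × 10.51 = 57.8, so 58 per group. This reproduces. With 20% dropout, 58 / 0.8 = 72.5, so 73, close to the stated 75. Conversely, 75 × 0.8 = 60 evaluable per group.

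**What a non-significant result would leave open (60 per arm).**
- Standard error of a difference: 7.3 × √(2/60) = 1.333.
- 95% half-width: 1.96 × 1.333 = 2.61.
- Observed shortfall 2.0: z = 2.0 / 1.333 = 1.50, P about 0.13 to 0.14, interval 2.0 ± 2.6 = -0.6 to 4.6. This contains 4.4.
- Any observed shortfall between 4.4 - 2.61 = 1.79 and 2.61 is non-significant and also fails to exclude 4.4. Below 1.79, the interval does exclude 4.4.

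**What the same size does if the question is exclusion of a shortfall** (one-sided 0.025; the margins are illustrative assumptions, since the protocol gives none).
- Margin 4.4, true difference 0: n = 2 × 7.3² / 4.4² × 10.51 = 57.8, so 58. Power is 90% at 58 and 91% at 60.
- Margin 4.4, true shortfall 4.4 (B gains 4, as assumed): 2.5% at 60.
- Margin 3.0, true difference 0: 2 × 7.3² / 3.0² × 10.51 = 124.4, so 125 per group before dropout. Power at 60 is 61%.
- Margin 2.2, true difference 0: 2 × 7.3² / 2.2² × 10.51 = 231.4, so 232 per group before dropout. Power at 60 is 38%.

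**Power beyond B v C (60 per arm, SD 7.3, two-sided 0.05).** The means for A are assumptions; B = 4 and C = 8.4 throughout. Pairwise power is Φ(difference / 1.333 - 1.96); ANOVA power is from the noncentral F distribution.

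| A gains | A v C | Three-group ANOVA |
|---|---|---|
| 4 | 91% | 93% |
| 5 | 72% | 88% |
| 6 | 43 to 44% | 84% |
| 6.2 (midway) | 37 to 38% | 84% |
| 8.4 | no difference to detect | 93% |

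Where a range is shown, the lower value uses the t distribution and the upper the normal. B v C itself is 91% at 60.

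**The 15 for time to recovery.** Difference 35 - 22.5 = 12.5 days, SD 6.2: 2 × 6.2² / 12.5² × 10.51 = 5.2, so 6, not 15. At SD 6.2, 15 corresponds to a difference of √(2 × 6.2² × 10.51 / 15) = 7.3 days. At 12.5 days, it corresponds to an SD of about 10.6. The cost figure of 24 cannot be checked, because no cost SD is given.

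**The case against.** The strongest reply is that Hypothesis 1 is a feasibility statement. It does not claim equal weight gain, and Sample Size openly expects slower gain at lower cost. Failure to respond, mortality, within-group growth and cost all bear on whether home management works, and the cost test runs in favour of home care. This stands. A reader might infer that no result of this trial could support its hypotheses, but the documents do not support that. The gap concerns the sized between-group tests of weight gain and time.

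A reader might also infer that the 0.05 holds for one pair only. It does not follow. It holds for each pair taken singly and for a single three-group ANOVA under the global null. With exactly three groups, testing pairs only after a significant ANOVA also controls the family-wise error. The protocol does not say that pairs will be tested without that gate, and the follow-up procedure is ordinary content for an analysis plan. Only the 90% is specific to B v C.

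Nor does any section say that P>0.05 will be read as support for home care. That is a risk left open by the missing criterion, not a stated rule.

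Finally, it is tempting to say that testing B v C and then A v C against a margin, in fixed order, keeps 90% power with no more children. It does so for B v C only at a 4.4 margin with no true difference. Under the protocol's own assumption for B it succeeds 2.5% of the time, and A v C would then almost never be reached.

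**Conclusion.** The point holds for weight gain and time to recovery. The binding calculation is a test for a deficit that the protocol assumes, and nothing links it to Hypothesis 1. At 60 evaluable per arm and SD 7.3, a non-significant result can coexist with an interval that reaches 4.4 g/kg per day, which is 4.4 / 8.4 = 52% of the hospital gain. The stated power is right for B v C and unsupported for A v C, where it is about 72% if A gains 5 and 43% if A gains 6. ANOVA power over the values examined runs from 84% to 93%. This is not a detail to be left to an analysis plan, because the hypothesis, the target difference and its meaning are all fixed in the protocol.

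The 15 for time is inconsistent with its printed inputs but immaterial, since 75 rests on the 58, which reproduces. It cannot be told from the document whether the 15, the difference or the SD is the misprint, so a flat correction to 6 would be a guess.

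**What to change.** Wording in two sections, with no change to the number of children.

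**Data Analysis.** Judge Hypothesis 1 by the 95% confidence intervals for C minus B and C minus A in weight gain, read against a largest acceptable shortfall stated and justified before enrolment. Say explicitly that P>0.05 is not support for home management.

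**Sample Size.** State that the 90% applies to B v C as a test for a difference. Give the assumed mean for A, or the A v C power over a range of means. State that 58 to 60 per group excludes a 4.4 shortfall with about 90% power only if home truly equals hospital, and with 2.5% if B truly gains 4. A tighter margin can therefore be addressed only by estimation at this size; confirming one would need more children. Reconcile the 15 for time to recovery with 22.5 v 35 days and SD 6.2.

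The downside is that the conclusion on Hypothesis 1 will rest on interval width and may be inconclusive.

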## Rationale

- If the hospital to home-based nutritional programme is found to be more cost-effective than the hospital-based programme, then it will be possible to rehabilitate more severely malnourished children with the same amount of available resources.
- It will be possible to extend the programme, if found to be effective, to other locations/health centres on a country-wide basis through governmental and non-governmental health care services.
- Home visits will provide health and nutrition education to the study mothers as well as neighbouring mothers, will help in the identification of medical problems and early referral of sick children to appropriate health centres.
- Active participation will help in confidence building of mothers on home management of severely malnourished children. Preparation and use of low-cost diets will help in preventing malnutrition among siblings as well as in subsequent children.

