### **Outcome Measures**

- Time to recovery (achievement of WH 80%, oedema-free), in days
- Rate of weight gain, in g/kg per day calculated from lowest weight to discharge weight
- Speed of loss of oedema, in days
- Failure to respond
- Morbidity, in number and duration of episodes over equal periods of follow-up for both groups
- Mortality
- Cost of treatment

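### Three outcomes are sized and seven listed, but none is named as deciding, although the planning assumptions themselves predict a result against home care on weight gain and for it on cost

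*Protocol*

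**What the plan says.** Sample Size (Protocol) says that the pair-wise comparisons of main interest should be settled first. It then gives planning values only for outpatient home care (treatment B) against hospital care (treatment C). For home care it assumes that it "will result in a relatively lesser weight gain of 4 g/kg per day" (hospital: 8.4, SD 7.3), "will require approximately 35 days to achieve WH >80" per cent (hospital: 22.5 days, SD 6.2), and will "lead to a 35% reduction in cost of treatment". Each outcome gets its own sample size: "Sample sizes of 58, 15, and 24 children in each group (hospital and home-based) were calculated from the assumptions of weight gain, time to achieve" the weight-for-height target, and cost. The level is given once, for these calculations: "power of detection is 90%, and type I error is 0.05". The largest figure, with 20% dropout, becomes 75 per arm.

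Outcome Measures lists seven items with no ranking. The first is "Time to recovery (achievement of WH 80%, oedema-free), in days", which is not the outcome that sets the sample size. The Project Summary, Specific Aims and the abstract for the Ethical Review Committee carry similar unranked lists and add growth.

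Data Analysis says: "The outcome variables will be compared both within and between groups from enrollment to discharge". It names ANOVA for normally distributed quantitative variables and chi-square for categorical ones. It gives no primary outcome, order, test level or contrast.

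The Rationale looks ahead to use of the result: "It will be possible to extend the programme, if found to be effective, to other locations/health centres on a country-wide basis". Its first bullet speaks of cost-effectiveness, and Clinical Economics plans a cost-benefit analysis from institutional and societal perspectives.

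**The concern.** A trial with several outcomes and no named primary is open to choosing the outcome afterwards. Two features make that more than a missing label here.

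First, the plan expects its sized outcomes to disagree: slower weight gain and later recovery at home, but lower cost. A reader who wants to call home care effective and one who wants to call it ineffective could each point to a significant, fully powered result. The trial is open: under Response to comments of reviewers the investigators accept that it cannot be blinded. Any choice made later would therefore be made with the arms known.

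Second, the only comparison that was sized (B against C) is not the one an overall three-group ANOVA tests.

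What is at stake is the meaning of effective in the Rationale, on which country-wide extension is to rest.

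**Working it through.** **Inputs.** From Sample Size: weight gain 8.4 against 4 (difference 4.4), SD 7.3; time 22.5 against 35 days (difference 12.5), SD 6.2; cost 35% lower, no SD given; error 0.05, power 90%; 75 per arm, 20% dropout, so 75 × 0.8 = 60 evaluable.

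**Reproducing the plan's figures.** Its formula is n = 2 × (SD/WD)² × (z for α + z for β)². With two-sided 0.05 and 90% power the factor is (1.960 + 1.282)² = 10.507.
- Weight gain: 2 × (7.3/4.4)² × 10.507 = 57.8, so 58 as stated. One-sided gives 47.1, so 48; the plan is therefore two-sided.
- Dropout: 58/0.8 = 72.5, so 73; 60/0.8 = 75. The stated 75 is consistent.
- Time: 2 × (6.2/12.5)² × 10.507 = 5.2, so 6. The stated 15 does not reproduce. This does not change the sample size, because 58 governs.
- Cost: with no SD, the stated 24 implies a standardised difference of √(2 × 10.507/24) = 0.936, that is an SD of 0.35/0.936 = 37% of mean hospital cost.

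**Power at 60 per arm, two-sided 0.05.**
- Weight gain (against home care): 0.906 by noncentral t.
- Time (against home care): above 0.999.
- Cost (for home care): 0.999 with the SD inferred from 24. Since that SD is an inference, I take a range as an assumption:

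| Cost SD, % of mean hospital cost | Power for cost |
|---|---|
| 30 | 1.00 |
| 37 | 0.999 |
| 50 | 0.97 |
| 60 | 0.89 |
| 75 | 0.72 |

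**Chance of opposite significant results (weight gain against, cost for).** Treating the two as independent: 0.906 × 1.00 = 0.91 at the top of the range and 0.906 × 0.72 = 0.65 at the bottom. With the inferred SD, correlation hardly matters: the lowest possible joint probability is 0.906 + 0.999 − 1 = 0.905.

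**False positives for B against C if each outcome is tested at 0.05 and nothing differs.** Independent outcomes: 1 − 0.95³ = 0.14 for three and 1 − 0.95⁷ = 0.30 for seven. Simulation with equally correlated normal statistics (400,000 draws):

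| Correlation | Three outcomes | Seven outcomes |
|---|---|---|
| 0 | 0.14 | 0.30 |
| 0.5 | 0.13 | 0.23 |
| 0.9 | 0.08 | 0.11 |

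**Overall ANOVA for weight gain, 60 per arm, B at 4.0 and C at 8.4.** Power depends on where home care with home follow-up (A) falls: 0.84 if midway, 0.87 if a quarter of the way from either arm, 0.93 if equal to B or to C. The planned B against C contrast within the same model has power 0.91 wherever A lies. A significant overall F does not say which arms differ.

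**Weight gain at 0.025**, as Holm may require: power 0.85.

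**The case against.** The strongest reply is that the conflict is deliberate and partly provided for. The protocol states two hypotheses, that children can be managed at home and that cost-benefit is better there. It openly assumes slower recovery at lower cost. Clinical Economics plans the analysis meant to bring the two together, and one Rationale bullet is about cost-effectiveness, not effect alone. That stands: a reader might infer that the plan overlooked the trade-off, and it did not. What it lacks is a named deciding outcome on the effect side and a statement of how effect and cost are to be read together.

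Other readings go further than the documents allow:
- That the plan tests all seven outcomes at 0.05. That level appears only in the sample-size calculation; Data Analysis gives none. The error rates above are conditional on it. They are also approximate, because a test of a rare event has a true size below 0.05: with mortality near the 3.5% cited in the investigators' reply to the Ethical Review Committee, about 0.04 uncorrected and 0.005 by an exact or continuity-corrected test. The all-null case is not what the plan expects either.
- That opposite results are certain. They are likely, and how likely depends on a cost SD the protocol does not give. Inferring it from 24 is less secure because the companion figure of 15 does not follow from its own inputs.
- That ANOVA costs power. The 0.84 is the worst position for A; at the other end ANOVA has 0.93, above the contrast. Naming ANOVA does not exclude contrasts. The lasting objection is that the overall test does not answer the question that was sized.
- That a test of weight gain settles Hypothesis 1. A significant result shows home care slower; a non-significant one does not show it adequate. No acceptable loss is stated.

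**Conclusion.** The point holds in this form. Three outcomes are sized, seven are listed, none is named as deciding, and the named analysis does not isolate the pair that was sized. On the plan's own weight-gain assumption, and a cost SD between 30% and 75% of mean hospital cost, about 65% to 91% of trials would give significant results in opposite directions. If 0.05 is used per outcome, the B against C false-positive chance is about 0.08 to 0.14 over three outcomes and 0.11 to 0.30 over seven, against a stated 0.05.

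Choosing the primary outcome belongs in the protocol, so this is not detail to leave to a later analysis plan. A reader might infer that the trial is too small or its data unsound; the documents do not support that, because 58 reproduces and 75 per arm covers dropout. What is not fixed in advance is the conclusion to be drawn.

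**What to change.** In Outcome Measures and Data Analysis:
- Name rate of weight gain, which already sets 75 per arm, as the primary outcome. Test it as a planned B against C contrast and report it with its 95% confidence interval.
- Name cost of treatment as the test for Hypothesis 2, with Holm across these two tests at 0.05 overall.
- Label the other outcomes, and the comparisons involving A, as secondary.
- State that a non-significant difference in weight gain does not show home care to be as good, that lower cost alone does not establish effectiveness, and that the effect and cost results are read together through the analysis in Clinical Economics.
- Define the closing weight for the weight-gain rate at the same endpoint in all arms. Outcome Measures uses the weight at discharge, but A and B leave the unit after 7 days while C leaves on passing the weight-for-height target, so the literal measure covers different periods.

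The cost is a few sentences and no extra children. The other outcomes and the A comparisons lose confirmatory status. If cost does not pass at 0.025, weight gain must, with power 0.85 in place of 0.91. If the sponsor prefers another deciding outcome, naming it in advance also closes the gap.
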